ordinal outcomes. The lineup procedure involves creating a plot assessing a given model assumption (e.g., normality of residuals) from both the analytic model and from several simulated models where the assumption is met. If a blinded observer cannot distinguish the analytic model plot from the simulated model plots, then the assumption has been met (Loy, Hofmann, & Cook, 2017). Given that 100 multiply-imputed datasets were used in the analysis, it is not practical to check model assumptions using all of them. Rather, a single dataset will be randomly selected and used. The lineup plots will be generated by the data analyst and inspected by members of the research team that are blinded to the location of the analytic plot.

The mixed-effect models for continuous outcomes will initially be estimated with a Gaussian distribution and an identity link (i.e., assuming a linear relationship). If the diagnostic lineup plots identify issues with residual non-normality, alternative robust methods will be evaluated. These methods include the use of a sandwich estimator with the LMM, such as that implemented in the R package `clubSandwich` (Pustejovsky, 2019). Alternatively, a generalised LMM with an appropriate distribution (e.g., gamma or inverse gaussian) could be used, such as those implemented in the R package `glmmTMB` (Brooks et al., 2017). A weighted generalised estimating equations (wGEE) model could be used, as implemented in the R package `wgeesel` (Xu, Li, & Wang, 2018). Finally, a two-stage analysis could also be used, as this has shown to be very robust to violations of distributional assumptions (Overall & Tonidandel, 2010; Senn, Stevens, & Chaturvedi, 2000).

Model Convergence

A common difficulty with LMM analyses is model convergence (Bates, Kliegl, Vasishth, & Baayen, 2015). Model convergence occurs when the iterative maximum-likelihood procedure has arrived at a stable set of estimates (i.e., there is minimal change in estimates with further iteration). However, when models have large numbers of random effects this optimisation process can then take a large number of iterations before it converges (Bates et al., 2015). Problems with convergence can also be exacerbated by the presence of unnecessary random effects in the model, that is, if there are random effects for parameters that have very little variance between individuals or groups. (Bates et al., 2015).

If issues with model convergence are encountered in the present analysis, the maximum number of iterations for the optimisation procedure will first be increased. If

increasing the number of iterations does not improve convergence, more parsimonious random effect structures will be used (e.g., removing the random intercept for group).

Model Parsimoniousness

The analytic approaches described have been chosen for their increased flexibility and minimal assumptions about the direction or nature of relationships between variables. However, given the additional number of parameters that need to be estimated, this flexibility may come at the cost of precision in the estimates. To assess whether the flexible modelling of time is needed, plots of the observed and model-estimated values at each measurement occasion will be inspected. If simpler model structures (e.g., linear splines) appear appropriate, the model will be re-fitted, and the estimates inspected. Similarly, the residual variance-covariance matrix of the residuals will be inspected to identify whether a more parsimonious structure would be appropriate (e.g., CAR1).

Multiple Imputation

To assess whether the imputation model was consistent with the observed data, the analysis results will be compared with the results of applying each model to the observed (partially missing) data. The estimates from the multiply-imputed and the observed data should be broadly consistent. If the estimates markedly differ from each other, this could indicate issues with either the imputation model or algorithm, or the presence of bias in estimates with partially missing data that has been corrected by the imputation model.

A key sensitivity analyses will be testing the sensitivity of the results to violations of the missing at random (MAR) assumption. As multiple imputation assumes that the data are MAR, the imputed values could be biased if this is not the case. In other words, if there is a systematic reason for why some individuals did not adhere to treatment, ignoring this when imputing their missing responses could bias the results away from the ‘true’ effect. A common means of testing this assumption is called a ‘tipping-point’ analysis (Mallinckrodt & Lipkovich, 2017). The tipping-point approach to sensitivity analysis is implemented by modifying the imputed data by increasing amounts and identifying the magnitude of changes in imputed data that would be required for the results to no longer be significant (Mallinckrodt & Lipkovich, 2017). This is achieved through the repeated use of what is called a ‘delta-adjustment’ of the imputed values (van Buuren, 2018). A delta-adjustment is simply the addition of a fixed value (delta) to every imputed response. In other words, this approach is

artificially raising or lowering the mean response of all non-adherent individuals. By using increasingly large values of delta (the fixed value), a sensitivity analysis can identify the extent to which the non-adherent individuals would need to differ in their response before there is no longer a significant difference between the treatment groups.

Summary of Confirmatory Analyses

Outcome	Analysis	Fixed Effects	Random Effects	Residual Covariance Structure
SPS & SIAS	Linear Mixed Model	
 • Baseline • Time (Categorical) • Treatment • Baseline*Time • Treatment*Time 	
 • Intercept (Group) 	
 • Unstructured • Heterogenous Variances
BFNES, PROMIS Anxiety & Depression	Linear Mixed Model	
 • Baseline • Time (Piecewise) • Treatment • Baseline*Time • Treatment*Time 	
 • Intercept (Group) 	
 • CAR1 • Heterogenous Variances
Diagnostic Status	Pooled Test of Difference in Proportions	N/A	N/A	N/A
Clinician-Rated Severity	Cumulative-Link Mixed Model	
 • Baseline • Time (Categorical) • Treatment • Baseline*Time • Treatment*Time 	
 • Intercept (Group) • Intercept • Time 	N/A

References

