Prior to the exploration and analysis of the trial data, a series of checks will be performed to assess whether there are any systematic issues with the entry of data and subsequent calculation of composite scores for each scale. Firstly, a subset of the data entry for the SIAS at pre-treatment and at the 1-month follow-up will be independently audited to ensure that the ratings have been accurately entered. Secondly, the composite scores for each scale will be calculated independently by two members of the research team and assessed for

consistency. By taking these measures, we can ensure that neither the data entry or data processing introduces bias into the analysis.

Two clients will be excluded from analyses due to intentionally providing invalid responses to questionnaires. The implausible responding was identified by the treating clinicians, who observed that the clients repeatedly provided invalid responses throughout the course of therapy. Examples include repeatedly rating outside the maximum of a scale, continually using the same response option to rate every item in a scale; and wildly inconsistent responses from week to week to measures of the same construct. The likely implausible responses were reviewed by a member of the research team ([name]) blind to treatment condition, who confirmed that they were consistent with invalid responding. The scores will therefore be removed to prevent biasing both the imputation process and analysis.

Reliability of Outcome Measures

Diagnostic Reliability

In order to assess the reliability of diagnoses, the SCID was re-evaluated by a second diagnostician in a random sample of approximately 20% of assessments across the baseline, 1-month, and 6-month follow-ups. We will report the % of agreement and two indices of inter-rater reliability: Cohen's Kappa and Gwet's AC1. Two indices of inter-rater reliability will be used as Cohen's Kappa can falsely return low values at very high levels of agreement (Gwet, 2008).

Composite Reliability of Self-Report Outcome Measures

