Trial Estimand and Missing Data

Estimand

In clinical trials, it is common that not all patients fully adhere to the prespecified treatment protocol (e.g., some patients may miss some treatment sessions). As a result, several different types of treatment effect can theoretically be estimated. These include the expected effect if all randomised participants had adhered or the treatment effect amongst only completers (among others, Mallinckrodt, Lin, Lipkovich, & Molenberghs, 2012). The *estimand* of an analysis refers to the type of conceptual effect that is being estimated (Mallinckrodt & Lipkovich, 2017). The present analyses will target the ‘de jure’ estimand,

which is the estimated treatment effect if all randomised individuals adhered to the treatment protocol. Mallinckrodt and Lipkovich (2017) recommend that analyses of the de jure estimand include (a) data from all randomised subjects, consistent with the intent-to-treat principle, and (b) all outcome data collected up to the point that a patient became non-adherent. In the present analyses, non-adherence will be defined as missing more than two consecutive treatment sessions. This means that analyses will utilise all data collected from all randomised subjects up until the point they became non-adherent (in contrast to a completer analysis, which uses data from only a subset of the randomised participants). Other estimands (e.g., de facto estimands) will be reported in subsequent papers. For more about estimands and their implications for data analysis, see Mallinckrodt et al. (2012).

Missing Data

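### The exclusion of two clients for invalid questionnaires leaves its scope unclear and, read plainly, also removes their two clinician-rated primary outcomes

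*SAP*

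**What the plan says.** Three parts of the SAP bear on this.

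- **Data Validity Checks.** The paragraph opens with "Two clients will be excluded from analyses due to intentionally providing invalid responses to questionnaires". The examples that follow all concern rating scales: values beyond the scale maximum, one response option used for every item, and erratic scores from week to week. On detection it says "The implausible responding was identified by the treating clinicians, who observed that the clients repeatedly provided invalid responses throughout the course of therapy". A research team member then reviewed the responses "blind to treatment condition, who confirmed that they were consistent with invalid responding". The paragraph ends: "The scores will therefore be removed to prevent biasing both the imputation process and analysis".
- **First Table 1 (outcomes for the first paper).** There are three primary outcomes. The SIAS is self-report. SCID-5 diagnostic status and the severity scale are both labelled clinician-rated.
- **Estimand.** "This means that analyses will utilise all data collected from all randomised subjects up until the point they became non-adherent". The only event that ends use of a subject's data is non-adherence: "non-adherence will be defined as missing more than two consecutive treatment sessions". Invalid responding is not mentioned.

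**The concern.** The stated reason covers questionnaires, but the opening sentence removes clients, and removes them from analyses in general. If an analyst follows that sentence, two randomised people drop out of the SCID-5 and clinician-severity analyses for a reason that does not concern those measures. That would be a post-randomisation exclusion affecting two of the three primary outcomes, in a plan that elsewhere claims consistency with intention to treat. If the analyst follows the closing sentence instead, only questionnaire scores go. The two readings give different primary analysis sets, and the SAP does not choose between them.

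The route to exclusion adds to the concern. The first flag came during therapy from people who presumably knew which treatment they were delivering. The SAP describes no screen of all participants against a fixed rule, and the criteria are given as examples without thresholds. Blinded confirmation protects against wrongly condemning a flagged client. It does not show that similar responders in the other arm were equally likely to be flagged.

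**Working it through.** The SAP gives no figure for the effect of this exclusion, so there is nothing to reproduce. The check is mainly a comparison of text, followed by illustrative arithmetic.

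**Text**

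1. Were the two clients randomised? The SAP does not say so outright. They responded over the course of therapy and were reviewed blind to condition, so it is a firm inference.
2. Does the Estimand section allow their removal? Its only stopping rule is missed sessions, and it has no exception or cross-reference for invalid responders. A total exclusion therefore conflicts with its all-randomised commitment.
3. Does the stated reason reach the clinician ratings? No example concerns a SCID-5 interview or a severity rating.
4. Does a planned sensitivity analysis cover it? The tipping-point analysis shifts imputed values only, and clients who are removed altogether have none. No planned run compares results with and without the two clients.

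**Size**

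Inputs: 2 clients excluded (Data Validity Checks); a target of at least 96 randomised (Trial Design section). Assumptions not in the SAP: 48 per arm, and a one-month diagnosis rate p of 30% to 70%.

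- Share of target: 2/96 = 2.1%. If both are in one arm: 2/48 = 4.2% of that arm.
- Let p be the rate among the 46 others in the arm. Restoring two clients, of whom a have the diagnosis, changes the rate by (46p + a)/48 − p = (a − 2p)/48.
  - p = 0.3: a = 2 gives 1.4/48 = +2.9 points; a = 0 gives −0.6/48 = −1.25 points.
  - p = 0.5: ±1/48 = ±2.1 points.
  - p = 0.7: a = 2 gives +1.25 points; a = 0 gives −2.9 points.
- Working from whole counts among 48 and dropping two gives nearly the same range, about 1.3 to 3.1 points. For example, 14/48 = 29.2% becomes 12/46 = 26.1%.
- If one client is dropped per arm, with opposite diagnoses and otherwise equal arms, the difference moves by 1/47 = 2.1 points.
- Standard error of the difference, √(2p(1−p)/48): 9.4 points at p = 0.3 or 0.7, and 10.2 points at p = 0.5. The largest shift is about 2.9/9.4 = 0.3 standard errors.
- Power for a difference in means, 48 against 47 per arm, at assumed standardised effects of 0.4, 0.5 and 0.6: 50.0% against 49.2%, 68.8% against 67.9%, and 83.6% against 82.9%. The loss is below one point each time.

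**The case against.** The strongest reply is that the paragraph already means what the fix asks for. It sits in a section about scale entry and composite scores, its subject is questionnaire responding, and its last sentence removes scores rather than people. That reading is tenable. It does not settle the matter, because the opening sentence says otherwise and the choice determines who enters two primary analyses.

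A second reply is that a specific, disclosed exception overrides a general statement. The exclusion was written down before the data were made available, while they were blinded and not collated. That is to the plan's credit and makes a results-driven choice unlikely. The Estimand wording is still literally untrue if the exclusion is total.

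A reader might go further and infer two things that the SAP does not support.

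- *That valid primary-outcome data are certainly being thrown away.* The SAP does not say that these two clients attended a follow-up interview, or that any ratings obtained were sound. Someone who deliberately falsifies questionnaires might also mislead an interviewer. The most that can be said is that the SAP gives no reason to discard the clinician ratings.
- *That the filter favoured one arm.* Nothing in the SAP suggests differential flagging. That treating clinicians knew the condition is itself an inference. Out-of-range ratings and uniform responding can be verified on the form, and a blinded reviewer confirmed the cases. What remains is that equal detection in the two arms has not been shown.

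**Conclusion.** The point holds as a defect of scope and consistency. The exclusion is not limited to the outcomes that its reason concerns, its opening and closing sentences permit different analysis sets, and the broad reading contradicts the Estimand section. No reason is given for dropping SCID-5 status or clinician-rated severity.

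The numerical effect is likely to be small: 2.1% of the target sample and, at worst under the assumptions above, about 3 points in one arm's diagnosis rate, or roughly 0.3 standard errors of the difference. That worst case needs both clients in the same arm with the same diagnosis. The case for change therefore rests on keeping the randomised comparison intact for two primary outcomes, not on power or a demonstrated bias. It also rests on the inferences that both clients were randomised and that the clinicians who flagged them knew the treatment.

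**What to change.** - In Data Validity Checks, state that both clients stay in the randomised set, that only their invalid self-report scores are set to missing, and that these are handled by the planned multiple imputation. This still keeps the bad scores out of the imputation and the analysis.
- State that any SCID-5 and clinician-severity ratings obtained from them stay in the primary analyses.
- Amend the Estimand section so that it acknowledges this treatment of invalid scores and the two sections agree.
- Add a sensitivity analysis of the two clinician-rated outcomes without these clients. This addresses the doubt about interview validity. A run on their raw questionnaire scores is not a workable alternative, because ratings beyond the scale maximum have no valid score and the PROMIS measures use IRT scoring.

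The cost is a few sentences and one extra analysis of two outcomes. The downside is that two clients' self-report outcomes rest on imputation. If their baseline questionnaires were also invalid, which the SAP does not say, that imputation would have to lean on treatment condition, clinician ratings and other auxiliary variables.

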The objective of this trial is to evaluate whether imagery-enhanced cognitive behavioural group therapy (IE-CBGT) is superior to standard verbally-based cognitive behavioural group therapy (VB-CBGT) for the treatment of social anxiety disorder (SAD). The study protocol is described in McEvoy et al. (2017).

To improve the reproducibility, transparency, and validity of clinical trial analyses, it has been recommended that clinical trialists create a statistical analysis plan (SAP; Gamble et al., 2017; Yuan et al., 2019). The SAP is intended to complement the trial protocol. According to Gamble et al. (2017), a SAP should contain a more technical and detailed elaboration of the main features of the trial analyses. We have followed this recommendation in preparing this SAP, and further adhered to guidelines about the content of SAPs described in Gamble et al. (2017) and Yuan et al. (2019).

The current plan has been prepared during August and October 2019, prior to the data being made available. The final follow-up data for the last treatment cohort will be collected in November 2019. All trial data was blinded and not collated at the time of writing this analytic plan. Treatment condition will remain masked to the data analyst until after the analyses described in this SAP have been conducted. The present analysis plan will be time-stamped and made publicly-available.

Some of the proposed analyses deviate from those described in the protocol paper (McEvoy et al., 2017). The main reason is to better comply with best-practices in the analysis of clinical trial data, some of which have changed since the trial was registered and protocol published (Mallinckrodt & Lipkovich, 2017). We will also be taking advantage of improved analytic techniques and software that have been developed during the study's data collection period. Recent reanalysis of data collected in pilot studies (prior to the RCT) has also informed the feasibility of different planned analytic approaches (Erceg-Hurn & McEvoy, 2018; McEvoy, Erceg-Hurn, Saulsman, & Thibodeau, 2015; McEvoy & Saulsman, 2014). The analyses in this SAP supersede those described in McEvoy et al. (2017).

Trial Design, Methods, and Selection of Outcomes

A comprehensive overview of the trial design, eligibility criteria, randomisation schedule, sample size, outcomes, and measurement schedule can be found in McEvoy et al. (2017). Therefore, that information is not repeated in depth here.

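### The two invalid responders were found only through their treating clinicians, who know the therapy they deliver; any patient with the same pattern who was not nominated would stay in.

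*SAP*

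**What the plan says.** The SAP section on data validity checks states: "Two clients will be excluded from analyses due to intentionally providing invalid responses to questionnaires". It describes how they came to notice: "The implausible responding was identified by the treating clinicians, who observed that the clients repeatedly provided invalid responses throughout the course of therapy". The signs are offered as illustrations, without a count or threshold: "Examples include repeatedly rating outside the maximum of a scale, continually using the same response option to rate every item in a scale", followed by marked week-to-week inconsistency on measures of one construct. Confirmation came next: "The likely implausible responses were reviewed by a member of the research team". That member was blind to treatment and agreed that the responding was invalid. The stated purpose of removing the scores is to keep bias out of the imputation and the analysis.

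The section's other two checks are that "a subset of the data entry for the SIAS at pre-treatment and at the 1-month follow-up will be independently audited" and that "the composite scores for each scale will be calculated independently by two members of the research team".

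On masking, the SAP's opening section says: "Treatment condition will remain masked to the data analyst until after the analyses described in this SAP have been conducted". It describes no masking of the clinicians who run the groups. The Estimand section says that "analyses will utilise all data collected from all randomised subjects up until the point they became non-adherent" and does not mention the two exclusions.

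**The concern.** The decision has two stages, nomination and confirmation, and only the second was blind. The SAP does not say in words that clinicians know the arm. However, they deliver one of two different group therapies, so they must. Nomination depends on how closely a clinician looked at the forms and on how an odd pattern was read. One of the three signs, inconsistency from week to week, needs judgement, and the SAP itself reports rapid symptom improvement during weekly treatment in its pilot data. A blinded reviewer who sees only nominated cases can lower the number of wrong exclusions but cannot raise the number of correct ones.

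The stated purpose, preventing bias, is met fully only if the same standard is applied to every randomised patient. If detection differed between arms, invalid data would remain in one arm and not the other. As the plan stands, a reader could not tell whether that happened.

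**Working it through.** The SAP gives no figure on this point to reproduce. The check has two parts: whether any other step covers unnominated patients, and how large the effect could be.

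**Does any other step screen everyone?**
- Audit of SIAS entry: covers a subset of forms at two time points and tests whether ratings were typed in correctly. A faithfully entered invalid form passes.
- Double calculation of composite scores: tests scoring, not response validity.
- Exploratory plots before longitudinal modelling: cover all patients and all outcomes and may show odd trajectories, but carry no exclusion rule.
- A search of the full data set before the decision: not possible, since the opening section says the data had not been collated when the SAP was written, yet the exclusions were already fixed at two.
- Tipping-point analysis: adds a fixed amount to imputed values only. It does not put the two clients' observed scores back.
- CONSORT flow chart: may list reasons for loss, but does not commit to exclusions for invalid responding by arm.

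No step applies the signs to other patients, and no analysis retains the two clients.

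**How large could the effect be?**
Inputs: 2 exclusions (Data Validity Checks); at least 96 randomised (trial design section). Assumptions: 48 per arm, both clients in one arm, and each *d* SD from that arm's mean in the same direction. The SAP gives none of these, nor an SD for the SIAS.

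1. Share excluded: 2/96 = 2.1% overall; 2/48 = 4.2% of one arm.
2. Shift in the arm mean, and so in the contrast, when *k* of *n* patients are dropped: *k·d/(n − k)*, here 2*d*/46.
   - *d* = 1: 0.04 SD
   - *d* = 2: 0.09 SD
   - *d* = 3: 0.13 SD
3. Standard error of the difference, ignoring covariates and clustering: √(2/48) = 0.20 SD. The shift is therefore about 0.2 to 0.6 of a standard error (0.0435/0.204 = 0.21; 0.130/0.204 = 0.64).
4. On the SIAS scale, if the distance were 15 to 30 points (assumed): 2 × 15/46 = 0.65 and 2 × 30/46 = 1.30 points.
5. Diagnosis rate in that arm, if the clients are dropped from this outcome too. At 30%, 14.4 of 48 are cases. Dropping two cases gives 12.4/46 = 27.0% (−3.0 points); dropping two non-cases gives 14.4/46 = 31.3% (+1.3 points). At 50% the shift is ±2.2 points, and 70% mirrors 30%.
6. Chance that two clients fall in the same arm if detection has nothing to do with arm: 47/95 = 0.49. The arm split of two cases therefore says little by itself about unequal detection.

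If there is one client in each arm, deviating equally and in the same direction, the shifts cancel.

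**The case against.** The plan has real safeguards. The exclusions were written down before the data were available, the analyst is masked, and a person blind to treatment confirmed the pattern. That confirmation guards against the worse error, in which a clinician who knows the arm removes a valid patient. Clinicians are also well placed to judge intent, which a program cannot establish. The SAP describes the pattern as repeated over the course of therapy and names two objective signs beside the judgemental one. All of this stands, and it limits the concern to missed cases and unequal detection.

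Three stronger readings are tempting, and the SAP does not support them:
- A reader might infer that other invalid responders are in the data. The SAP does not show that any exist.
- A reader might infer that vigilance differed by arm. The SAP does not say how many clinicians there were or whether the same ones ran both therapies. If they did, differences between clinicians need not line up with arm.
- A reader might count the whole shift from removal as harm. If the two clients' responses were invalid, removing them brings the arm mean closer to the truth.

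The objection does not answer the central point: a blinded review confined to nominated cases does not make the selection blind.

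**Conclusion.** The concern holds as a limited weakness in how cases were found. Detection was by clinicians who know the therapy, only nominated responses were reviewed blind, and nothing in the plan would find or remove an unnominated patient with the same pattern.

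The size is probably modest: about 0.04 to 0.13 SD on the contrast against a standard error of about 0.20 SD, under the assumed 48 per arm, both clients in one arm, and distances of 1 to 3 SD. These figures give the movement caused by removal. They become bias only if the removal was mistaken; unequal detection by arm would add a bias of unknown size from invalid data left in. The SAP allows neither to be judged, because it gives neither the clients' arm nor a screen of the remaining patients. The point is a cheap improvement to the plan and does not show that the result is biased.

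**What to change.** Before unmasking, add to the data validity section:

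1. Screen the item-level questionnaire data of all randomised patients by program for the two objective signs: repeated out-of-range ratings, and the same option for every item across repeated questionnaires. State the counts that trigger a flag.
2. Have the same blinded team member review every flagged case by the same standard. Use week-to-week inconsistency only as supporting evidence in that review, not as an automatic limit. An automatic limit would flag genuine rapid change, and it cannot be applied weekly to the SIAS, whose post-baseline measurements are at weeks 4, 8 and 12 and the two follow-ups.
3. Set confirmed invalid questionnaires to missing.
4. Report the numbers flagged and excluded by arm.
5. Add a SIAS sensitivity analysis with the two clients' scores retained, using in-range values only.
6. Adjust the Estimand wording on all randomised subjects so that it acknowledges these exclusions.

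The cost is SAP wording, a short script on data already held, and some time from the existing reviewer. A few more questionnaires may become missing. The counts would be set after two cases are already known, so they should be fixed before the item data are screened.
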